6.2.1. Long-Term Treatment Visit Schedule

After completion of the Cycle 18 Day 1 (51 weeks on study treatment) visit, the frequency of study visits conducted at the investigative site may be extended to every 3 cycles (9 weeks) if the following criteria are met and the study site receives medical monitor approval:

- The subject has no ongoing \geq Grade 3 TEAEs or \geq Grade 2 treatment-related TEAEs.
- The subject has maintained an overall response of PR or better for at least 3 consecutive assessments.
- The subject has maintained a CCyR for at least 3 consecutive assessments.

- Women of childbearing potential must agree to have monthly pregnancy testing performed at home or at a local laboratory and must immediately notify the study site of a positive result so study medication can be held while a serum pregnancy test is performed. Urine pregnancy test kits may be provided to subjects.

In the interval between visits to the study site, sites must conduct remote/telemedicine visits with the subjects on Day 1 of each cycle (\pm normal visit window) to assess AEs, concomitant medications, ECOG performance status, and study medication compliance. Likewise, subjects must complete the scheduled laboratory assessments at a laboratory convenient to their homes. Data from these remote/telemedicine visits as well as the laboratory data collected will be entered into the eCRF at their respective cycle visits.

Subjects who may be eligible to switch to this long-term treatment visit schedule but have already surpassed Cycle 18 at the time of Protocol Amendment 6 may begin following this schedule in conjunction with a cycle that has the same assessments as Cycle 18 (eg, in conjunction with an eye exam), if the above criteria are satisfied.

Subjects may revert back to attending every study visit at the investigative site as needed (eg, to manage a new or worsening adverse event) but must always resume the extended investigative site visit schedule in conjunction with a cycle that has the same assessments as Cycle 18.

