7.6.2. Bone Marrow Exams and Cytogenetics

Bone marrow examinations are an integral part of assessing subject response to treatment and will be collected according to the following parameters:

- The components of a complete bone marrow exam will consist of a core biopsy, marrow aspirate, and associated peripheral blood smear slides. Every reasonable effort should be made to perform a complete exam at each disease assessment, however instances where all exam components cannot be obtained (eg, aspirate is a dry tap or core biopsy is contraindicated) will not be considered protocol deviations.
- Bone marrow exams will be conducted according to the schedule provided in [Table 7](#) and continue until disease progression or the completion of the disease follow-up period (Section [6.4.2](#)).
- Subjects who successfully bridge to HSCT should continue to have bone marrow examinations and peripheral blood smears, CBCs, and differentials assessed according to local standard of care.

Table 7: Bone Marrow Exam Schedule

Study Phase	Exam Frequency
Screening (baseline)	
• Obtained within 6 weeks of enrollment (Cycle 1 Day 1).
Treatment	
• After 6 (\pm 1) weeks (just prior to Cycle 3) and then every 9 (\pm 1) weeks from Cycle 1 Day 1 for the first 12 months (eg, until Week 51/Cycle 18) on treatment.• After 12 months on treatment, every 18 (\pm 1) weeks for subjects who have not yet achieved CCyR or every 52 (\pm 2) weeks for subjects who have a confirmed CCyR. If progression is suspected in peripheral blood, a bone marrow biopsy and bone marrow aspirate should be conducted as an unscheduled visit as soon as possible.
Disease status follow-up	
• Subjects who enter the disease status follow-up for reasons other than to bridge to transplant may continue to have disease assessments according to the schedule above.• Subjects who bridge to transplant should have bone marrow examinations and peripheral blood smears, CBCs, and differentials at 1 to 3 months and 6 months post-transplant and then as per local standard of care. Slides from these exams will be forwarded to the central pathologist for review.

Flow cytometry is not a required component of the bone marrow exam; however, if it is performed, the results should be captured in the eCRF.

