9.4.1.3. Other Efficacy Analysis

Myeloproliferative Neoplasm Symptom Assessment Form and EORTC QLQ-30 measurements and change from baseline to each visit where MPN-SAF or EORTC QLQ-30 is measured will be summarized descriptively.

The number of subjects with SD who achieve CHR, marrow response, or clinical benefit, as determined by as determined by investigator assessment according to the response criteria in [Appendix E](#) will be summarized.

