APPENDIX E. RESPONSE CRITERIA FOR MYELOID/LYMPHOID NEOPLASMS WITH FGFR1 REARRANGEMENT

Table E1: Response Criteria

Response Subcategory	Response Criteria
CR ^a	
Presence of all of the following improvements:
 
 1. Bone marrow: $\leq 5\%$ myeloblasts (including monocytic blast equivalent) and no lymphoblasts, with normal maturation of all cell lines, and return to normal cellularity^b. 2. Osteomyelofibrosis absent or equal to "mild reticulin fibrosis" (Grade 1 or less fibrosis)^c 3. Peripheral blood^d 
 - WBC $\leq 10 \times 10^9$ cells/L. - Hgb ≥ 11 g/dL. - Platelets $\geq 100 \times 10^9/L; \leq 450 \times 10^9/L$. - Neutrophils $\geq 1.0 \times 10^9/L$. - Blasts = 0%. - Neutrophil precursors reduced to $\leq 2\%$. - Monocytes $\leq 1 \times 10^9/L$. - Eosinophils $\leq 0.5 \times 10^9/L$. 4. Extramedullary disease: Complete resolution of extramedullary disease present before therapy (eg, lymphadenopathy), including palpable hepatosplenomegaly. 
NOTE: Persistent low-level dysplasia is permitted given subjectivity of assignment of dysplasia^b.

PR	
Presence of all of the following improvements:
 
 1. Reduction of bone marrow blasts (and blast equivalents) by 50%, but remaining $> 5\%$ of cellularity (except in cases with $\leq 5\%$ bone marrow blasts at baseline). 2. Normalization of peripheral blood indices listed in CR Criterion 3. 3. Extra medullary disease response of CMR/CR or PMR/PR (see Table E2).
Progression of disease	
Combination of 2 major criteria, 1 major and 2 minor criteria, or 3 minor criteria from following lists:
 
Major criteria:
 
 • Increase in blast counta 
 ○ $< 5\%$ blasts: $\geq 50\%$ increase and to $> 5\%$ blasts. ○ 5%-10% blasts: $\geq 50\%$ increase and to $> 10\%$ blasts. ○ 10%-20% blasts: $\geq 50\%$ increase and to $> 20\%$ blasts. ○ 20%-30% blasts: $\geq 50\%$ increase and to $> 30\%$ blasts. • Evidence of cytogenetic evolution 
 ○ Re-appearance of a previously present or appearance of a new cytogenetic abnormality in complete cytogenetic remission via classic karyotyping or FISH. ○ Increase in cytogenetic burden of disease in partial cytogenetic remission by $\geq 50\%$ via classic karyotyping or by $\geq 50\%$ and involving at least 10% (eg, 2/200) of cells via FISH.

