Table E1: Response Criteria (Continued)

Response Subcategory	Response Criteria
Progression of disease (continued)	
 • New or worsening extramedullary disease 
 ○ Worsening splenomegaly 
 ▪ Progressive splenomegaly that is defined by IWG-MRT: the appearance of a previously absent splenomegaly that is palpable at > 5 cm below the left costal margin or a minimum 100% increase in palpable distance for baseline splenomegaly of 5 to 10 cm or a minimum 50% increase in palpable distance for baseline splenomegaly of > 10 cm. ○ Extramedullary disease outside of the spleen. 
Minor criteria:
 
 • Transfusion dependence.^e • Significant loss of maximal response on cytopenias $\geq 50\%$ decrement from maximum remission/response in granulocytes or platelets. • Reduction in Hgb by $\geq 1.5\text{ g/dL}$ from best response or from baseline as noted on complete blood count. • Evidence of clonal evolution (molecular).
Stable disease	
Meeting neither progression of disease nor response criteria.
 
Subjects with stable disease will be further characterized according to criteria presented in Table E3.

Cytogenetic Response^f	
Complete (cCyR)	0% 8p11 translocated metaphases as seen on classic karyotyping with minimal of 20 metaphases, or FISH.
Partial (pCyR)	Decrease from baseline of 50% or more 8p11 translocated metaphases as seen on classic karyotyping with minimal of 20 metaphases, or FISH.

CR = complete response; FISH = fluorescence in situ hybridization; Hgb = hemoglobin; IWG-MRT = International Working Group-Myeloproliferative Neoplasms Research and Treatment; PR = partial response; WBC = white blood cell.

^a Given the current lack of a validated tool to assess complete resolution of symptoms, "CR with resolution of symptoms" (a complete resolution of disease-related symptoms as noted by the MPN-SAF in presence of CR) will be a provisional category of disease response.

^b Presence of dysplastic changes, which may be interpreted within the scope of normal range of dysplastic changes, may still exist in the presence of CR as allowed in MDS IWG. Marrow should exhibit age-adjusted normocellularity in CR.

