Marrow response	
 Complete marrow response: Presence of all marrow criteria listed in CR criterion without normalization of peripheral blood indices listed in CR Criterion 2. Partial marrow response: Bone marrow blasts (and blast equivalents) reduced by 50%, but remaining $> 5\%$ of cellularity, or reduction in grading of reticulin fibrosis from baseline on at least 2 bone marrow evaluations spaced at least 2 months apart.
Clinical benefit	
Requires 2 of the following in the absence of progression or CR/PR and independent of marrow response (peripheral blood response must be verified at ≥ 8 weeks) to be considered a clinical benefit:
 
Erythroid response:
 
 Hgb increase by ≥ 2.0 g/dL. TI for > 8 weeks for patients requiring at least 4 packed red blood cell transfusions in the previous 8 weeks. Only red blood cell transfusions given based on physician's judgment for a pretreatment Hgb of ≤ 8.5 g/dL will count in the red blood cell TI response evaluation.^a 
Platelet response:
 
 Transfusion independence when previously requiring platelet transfusions of at least a rate of 4 platelet transfusions in the previous 8 weeks. Pretreatment $\leq 20 \times 10^9/L$: Increase from $< 20 \times 10^9/L$ to $> 20 \times 10^9/L$ and by at least 100%. Pretreatment $> 20 \times 10^9/L$ but $\leq 100 \times 10^9/L$: absolute increase of $\geq 30 \times 10^9/L$.^a 
Neutrophil response:
 
 Pretreatment $\leq 0.5 \times 10^9/L$: At least 100% increase and an absolute increase $\geq 0.5 \times 10^9/L$. Pretreatment $> 0.5 \times 10^9/L$ and $\leq 1.0 \times 10^9/L$: At least 50% increase and an absolute increase $\geq 0.5 \times 10^9/L$.^a 
Eosinophil response:
 
 Normalization if pretreatment $> 0.5 \times 10^9/L$.^a 
Extramedullary disease response:
 
 As defined in Table E2.
Symptom response	Improvement in symptoms as noted by decrease of $\geq 50\%$ as per the MPN-SAF scoring; subjects scoring < 20 at baseline were not considered eligible for measuring clinical benefit.

CR = complete response; CHR = complete hematologic response; Hgb = hemoglobin; PR = partial response; TI = transfusion independence.

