- 5. Section 6, Study Assessments (Table 4: Study Assessments); Section 7.5.5, Comprehensive Eye Examination**

Description of change: Language added to indicate that OCT is mandatory at baseline and every 3 cycles and EOT as part of the eye examination process.

Rationale for change: Required program-wide per FDA feedback.

6. Synopsis; Section 6, Study Assessments (Table 4: Study Assessments; Table 5: Laboratory Assessments); Section 7.6, Efficacy Assessments

Description of change: Section edited to provide greater detail regarding efficacy assessments.

Rationale for change: To clarify section for investigators.

7. Appendix D, Response Criteria for Myeloid/Lymphoid Neoplasms With FGFR1 Rearrangement

Description of change: Deleted osteomyelosis grading as a criterion for partial response.

Rationale for change: The criterion is not needed in the definition of a partial response.

8. Incorporation of administrative changes. Other minor, administrative changes and clarifications have been incorporated throughout the Protocol and are noted in the redline version of the amendment.

Amendment 4 (22 MAY 2019)

Overall Rationale for the Amendment:

The main purpose of this amendment is to modify the primary and secondary study efficacy endpoints and to revise the proposed response criteria. Other modifications have been made to include treatment-naïve subjects and to update the Protocol with program-level standard language.

1. Synopsis; Section 1.1.2, Myeloid/Lymphoid Neoplasms With FGFR1 Rearrangement; Section 2, Study Objectives and Endpoints; Section 9.2, Selection of Sample Size; Section 9.4.1, Efficacy Analyses

Description of change: The primary efficacy endpoint was modified to include only the proportion of subjects who achieve a complete response. Secondary endpoints measuring the rates of response and cytogenetic response were added, as were secondary endpoints of duration of complete response and duration of response. An exploratory efficacy endpoint to describe potential indicators of clinical benefit in subjects [REDACTED]

Rationale for change: To evaluate the efficacy of study treatment according to a more conventional endpoint.

2. Appendix D, Response Criteria for Myeloid/Lymphoid Neoplasms With FGFR1 Rearrangement

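### The partial response rule in Protocol Table E1 and SAP Table A1 requires marrow blasts to stay above 5%, so some deeper responders become stable disease; the FISH progression cut-off beside it contradicts itself tenfold

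*Protocol*

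**What the plan says.** Protocol Appendix E (Table E1) and SAP Appendix A (Table A1) carry the same response rules.

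- **PR** needs three things together. Item 1 is "Reduction of bone marrow blasts (and blast equivalents) by 50%, but remaining" above 5% of cellularity, with an exception for baseline blasts of 5% or less. Item 2 is normalization of the CR blood indices. Item 3 is a complete or partial response of extramedullary disease (EMD).
- **CR** needs myeloblasts at or below 5% and no lymphoblasts, normal maturation and cellularity, fibrosis of Grade 1 or less, normal blood indices, and complete resolution of EMD.
- **Stable disease** is the remainder: "Meeting neither progression of disease nor response criteria".
- **Progression** needs 2 major criteria, 1 major and 2 minor, or 3 minor. One form of the cytogenetic major criterion applies in partial cytogenetic remission. By FISH it asks for a rise of at least 50% that involves at least 10% of cells, and it gives 2/200 as the example.

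Table E3 subdivides stable disease. Clinical benefit there "Requires 2 of the following in the absence of progression or CR/PR and independent of marrow response". Partial marrow response has the same 5% floor on blasts, or alternatively "reduction in grading of reticulin fibrosis from baseline on at least 2 bone marrow evaluations spaced at least 2 months apart". Protocol 9.4.1.3 summarizes "The number of subjects with SD who achieve CHR, marrow response, or clinical benefit" as a separate item.

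Best response of CR or PR is the first listed secondary endpoint (Protocol 2.2.2, SAP 7.3) and decides who enters DOR. Protocol 6.2.1 also makes it a condition for the long-term visit schedule: "The subject has maintained an overall response of PR or better for at least 3 consecutive assessments".

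**The concern.** Normally a partial response category catches everyone who improves enough but falls short of complete response. Here it has a gap. Once blasts reach 5% or less, a participant who misses any other CR item no longer meets PR item 1 either and drops to stable disease. The deeper marrow response gets the worse label.

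This runs against the rest of the table. PR item 3 accepts a partial EMD response, so residual EMD is meant to be compatible with PR. When Amendment 5 removed fibrosis grading from PR, its stated reason was: "The criterion is not needed in the definition of a partial response". Yet with blasts at or below 5%, residual EMD or fibrosis above Grade 1 now blocks PR, unless baseline blasts were already 5% or less.

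At stake are the CR+PR rate, membership and start of DOR, and access to the reduced visit schedule. The FISH conflict puts at stake whether two investigators would read the same low count alike when they judge progression, which feeds PFS and both duration endpoints.

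**Working it through.** **1. PR window.** For baseline blasts b above 5%, item 1 requires a later value a with a ≤ b/2 and a > 5%. The window is (5, b/2], which is empty when b/2 ≤ 5, that is, when b ≤ 10.

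| Baseline b | Values of a that meet PR item 1 |
|---|---|
| 6%, 8%, 10% | none |
| 12% | above 5% to 6% |
| 20% | above 5% to 10% |

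**2. Example participants** (normal blood counts, no progression):

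| Blasts | Other findings | As written | Floor removed |
|---|---|---|---|
| 20% to 10% | partial EMD response | PR | PR |
| 20% to 3% | partial EMD response | SD | PR |
| 20% to 3% | Grade 2 fibrosis, EMD resolved | SD | PR |
| 20% to 3% | maturation or cellularity not normal | SD | PR |
| 8% to 4% | partial EMD response | SD | PR |
| 20% to 3% | all other CR items met | CR | CR |

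No CR classification changes, so the primary endpoint does not move.

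**3. Who is affected, by endpoint.**

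- *Best response.* A participant who has once met all PR items inside the window keeps a best response of PR. Item 2 imports the blood criterion and its footnote, so counts must also hold on 2 analyses over at least 8 weeks. Marrow is examined at week 6 and then every 9 "weeks from Cycle 1 Day 1 for the first 12 months", so a fast responder can pass through the window unseen. The floor therefore costs a PR only to those never seen to meet PR inside it, including everyone with a baseline above 5% up to 10%.
- *DOR.* These participants are left out, or start late if they reach CR later. An earlier PR that deepens to 5% or less does not end DOR, because stable disease is not progression.
- *Visit schedule.* The response must be maintained at 3 consecutive assessments. Here an earlier PR who deepens to 5% or less without CR can also lose out. The schedule separately requires complete cytogenetic response at 3 assessments, which narrows this group.

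**4. Does Table E3 repair it?** No. Complete marrow response applies only without normal blood indices, which excludes these participants. Complete hematologic response, clinical benefit and the fibrosis-based partial marrow response may still be recorded. They sit within stable disease and do not count in CR+PR.

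**5. Size for CR+PR.** One participant is 1/46 = 2.2 points, or 1/47 = 2.1 points for the 47 treated by April 2023 (Protocol 1.3.2). The SAP's FDA population is limited to participants with prior systemic therapy and its size is not given; at an assumed 30, one participant is 1/30 = 3.3 points. For scale, if 23 of 46 responded (assumed), the Clopper-Pearson 95% interval is 34.9% to 65.1%, a half-width of 15.1 points. No baseline blast distribution is given, so the number affected cannot be computed. An assumed range of 0 to 5 gives 0 to 5/46 = 10.9 points.

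**6. FISH.** 2/200 = 1%, and 10% of 200 = 20 cells, a tenfold conflict. Counts of 2 to 19 per 200 (1.0% to 9.5%) meet one reading and fail the other. To see which value is workable, take two independent 200-cell counts at the same true burden p, with X1, X2 ~ Binomial(200, p) and X1 ≥ 1, and compute P(X2 ≥ 1.5·X1 and X2 ≥ cut-off). Probe error is ignored.

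| True burden | Cut-off 2/200 | Cut-off 20/200 |
|---|---|---|
| 2% | 30.2% | below 0.001% |
| 5% | 19.7% | 0.2% |
| 8% | 13.0% | 6.9% |
| 20% | 2.5% | 2.5% |
| 30% | 0.5% | 0.5% |

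The choice matters at low burdens and makes no difference at 20% or more.

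**The case against.** The strongest reply is that the effect may be nil. The primary endpoint is untouched, SAP 7.1 states no efficacy hypothesis, and no document shows that even one participant falls in the gap. That stands: the 0 to 5 range is illustrative.

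The floor might also be deliberate. The criteria adapt a published set (Protocol 1.1.2) and were revised on expert feedback (Amendment 4). But no reason is given for ranking 3% below 10%, and the rule conflicts with PR item 3 and the Amendment 5 rationale.

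Central review produces its own CR+PR, DOR and PFS (SAP 7.4), using criteria specific to baseline disease category (Protocol 7.6). This helps, but it runs beside the investigator-assessed endpoints and does not replace them.

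On FISH, the 10% is the rule and the example probably a typing slip. That is likely, and partial cytogenetic remission needs only a 50% fall, so burdens can be well above the range where the conflict matters. The documents still do not settle which figure is meant.

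A fair caution concerns the remedy. The exception for baseline blasts of 5% or less can be read as waiving only the floor or the whole of item 1. A rewording should not settle that silently. Nor should the Protocol rule change while participants are being assessed, because the reported endpoint would then mix two definitions.

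**Conclusion.** The concern holds on the text of both documents. The floor makes PR unreachable for baselines above 5% up to 10%. For higher baselines, it puts some deeper marrow responders below shallower ones. Compared with the same rule without a floor, it can only lower CR+PR, by 2.2 points per affected participant at N=46, with the number affected unknown and possibly zero. The FISH cut-off is inconsistent by a factor of ten, with a limited effect.

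Three stronger readings are tempting and are not supported:

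- That the CR rate is misestimated. CR does not use the floor.
- That every participant who reaches 5% or less is misclassified. Those who meet all other CR items are CR, those with baseline blasts of 5% or less fall under the exception, and those already seen to meet PR keep that best response.
- That the FISH conflict alone produces false progressions. It needs another major or two minor criteria.

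The classifications follow from the table wording alone. Only the overall size and the FISH noise figures rest on assumptions. This should be corrected before database lock, but it does not threaten the trial's main conclusion.

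**What to change.** 1. In both documents, correct the FISH example to 20/200, unless the sponsor confirms that 1% was intended.
2. By SAP amendment before database lock, add a supplementary derivation of best response, CR+PR rate and DOR. In it, PR item 1 becomes a blast reduction of at least 50%, whether or not blasts end at or below 5%. Keep the exception for baseline blasts of 5% or less as worded, and ask the sponsor to state whether it waives only the floor or the whole item. Remove the same floor from the blast-based partial marrow response in Table A3 within this derivation.
3. Keep investigator assessments under the current criteria as the reported secondary endpoints for all participants, and do not change the Protocol PR rule mid-study.
4. Editorial only: in Tables E3 and A3 the reference to CR Criterion 2 for blood indices should be to Criterion 3 (Criterion 2 is fibrosis), and in SAP Table A1 the reference to Table D2 should be to Table A2.

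The cost is a few words in the tables and one derivation from marrow, blood and EMD data that the SAP already lists in Appendix C. The drawback is that the derivation can only raise CR+PR and would be specified with open-label data in hand. It must therefore be labeled supplementary and shown beside the original result.

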7.6. Efficacy Assessments

See [Appendix F](#) for COVID-19-related guidance.

Investigators will assess response to treatment by evaluation of local peripheral blood results, bone marrow pathology, cytogenetics, and imaging for EMD at the frequencies listed below and according to the response criteria listed in [Appendix E](#). Investigative sites will also ship slides and samples to central labs as described below.

In addition, a Central Review Committee composed of hematopathologists and hematologists will be convened to conduct a retrospective review and adjudication of baseline diagnosis, baseline disease category (chronic phase without EMD, chronic phase with EMD, blast phase without EMD, blast phase with EMD, EMD only, or any additional categories as judged by the CRC), and response to treatment according to criteria specific to the baseline disease category. Details of the Committee's organization, responsibilities, and the adjudication processes can be found in the Committee Charter.

The interval schedule for the bone marrow and imaging assessments should be anchored to the start of study drug (Cycle 1 Day 1) and should not be delayed due to delays in cycle starts resulting from study drug interruption.

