Target	5PS score of 4 or 5 with reduced FDG uptake compared to baseline and residual masses of any size. Note: Reduced uptake defined as $\geq 25\%$ decrease in $\% \Delta \text{SUV}_{\text{max}}$.	$\geq 50\%$ decrease from baseline in SPD of all target lesions.
Non-target		No increase.
New lesions	None.	
NMR/SD		
Target	5PS score of 4 or 5 with no significant change in FDG uptake compared to baseline and residual masses of any size. Note: "No significant change in uptake" defined as the criteria of PMR/PMD not being met.	$< 50\%$ decrease from baseline in SPD of all target lesions. No PD criteria met.
Non-target		No progression.
New lesions	None.	
PMD/PD		
Target	5PS score of 4 or 5 with significant increase in FDG uptake, defined as $\geq 50\%$ increase in the $\% \Delta \text{SUV}_{\text{max}}$ of the most FDG-avid disease.	Node or lesion must be abnormal with an LDi > 15 mm, an increase by $\geq 50\%$ from nadir PPD, and an increase in LDi or SDi from nadir by: 
• At least 5 mm for lesions measuring ≤ 20 mm or• At least 10 mm for lesions measuring > 20 mm.
Non-target		Unequivocal progression.
New lesions	New or recurrent markedly diffuse FDG-avid uptake in the liver or spleen.	
• Regrowth of previously resolved lesions.• New node > 1.5 cm in any axis.• New extranodal site > 1.0 cm in any axis.

5PS = Deauville 5-point scale; CMR = complete metabolic response; CR = complete response; CT = computed tomography; FDG = fludeoxyglucose; LDi = longest transverse diameter of lesion; NMR = no metabolic response; PD = progressive disease; PET = positron emission tomography; PMD = progressive metabolic disease; PMR = partial metabolic response; PPD = product of perpendicular diameters; PR = partial response; SD = stable disease; SDi = shortest axis perpendicular to LDi; SPD = sum of product of perpendicular diameters of multiple lesions; SUV = standardized uptake value.

Table E3: Characteristics of Stable Disease

Characteristic	Criteria
CHR	Peripheral blood normalization as in CR Criterion 3 (Table E1 ; peripheral blood response must be verified at ≥ 8 weeks)

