Progression-free survival is defined as the time from the first date of taking study drug until the date of disease progression, as measured by response criteria or until death due to any cause, whichever is earlier. Participants who are still alive without experiencing disease progression at the time of analysis will be censored at the date of the last response assessment before the cutoff date. Participants who start a new cancer therapy or have stem cell transplant before disease progression will be censored at the date of last response assessment before new cancer therapy start or transplant. Progression-free survival data will be analyzed by the Kaplan-Meier method. The 95% CI will be calculated using the Brookmeyer and Crowley's method ([Brookmeyer and Crowley 1982](#)).

Overall survival is defined as the time from the first day of taking study drug until death due to any cause. Participants without death observed at the time of the analysis will be censored at last date known to be alive. Overall survival will be analyzed by the Kaplan-Meier method. The 95% CI will be calculated using the Brookmeyer and Crowley's method ([Brookmeyer and Crowley 1982](#)).

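### Growing extramedullary disease alone does not count as progression, so investigator-assessed PFS and duration of response may miss or delay events in subjects with extramedullary-only disease

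*Protocol*

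**What the plan says.** **Overall progression.** Table E1 of Protocol Appendix E, repeated in SAP Table A1, requires a "Combination of 2 major criteria, 1 major and 2 minor criteria, or 3 minor criteria". There are three major criteria: an increase in blasts, cytogenetic evolution, and "New or worsening extramedullary disease". Worsening spleen and "Extramedullary disease outside of the spleen" are sub-items of that third criterion. The four minor criteria are transfusion dependence, loss of response in granulocytes or platelets, a hemoglobin fall, and molecular clonal evolution. Stable disease is the default: "Meeting neither progression of disease nor response criteria".

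**EMD-level progression.** Table E2 (SAP Table A2) has its own PMD/PD rows, for example by PET-CT a "5PS score of 4 or 5 with significant increase in FDG uptake, defined as" a stated SUV increase. By CT it covers lesion growth or new lesions above stated sizes. The PR row of Table E1 refers to Table E2. SAP Table A1 labels this reference Table D2, which can only mean A2. The progression row makes no such reference.

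**Who is affected.** Protocol 7.6 lists the baseline categories for central review, including "blast phase with EMD, EMD only, or any additional categories as judged by the CRC".

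**Endpoints.** SAP 7.3 runs PFS from first dose "until the date of disease progression, as measured by response criteria", or to death. Duration of CR and duration of response end at progression or death. For all three, a subject who starts new therapy or has a transplant before progression is censored at the last prior response assessment.

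**The concern.** Marrow-based criteria suit disease that lives in the marrow. A subject whose disease is only in nodes or other extramedullary sites can have clear growth on imaging, meet PMD/PD in Table E2, and still be stable disease in Table E1. The remaining criteria are blood, marrow or clonal findings that such growth need not produce.

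The tables are also asymmetric. Shrinkage graded by Table E2 is part of the PR definition and so can help start the duration-of-response clock. Regrowth graded by the same table cannot stop that clock by itself.

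At stake is the reading of the investigator-assessed secondary time-to-event endpoints. A subject with growing EMD either stays at risk as event-free or changes therapy and is censored. Censoring because the disease is growing is informative. It removes the subjects with the worst course and treats them as if their later course were average.

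**Working it through.** **Plan's own figure.** The plan states none for PFS or duration of response. Its only probability statement concerns the CR rate (more than 80%). It reproduces at 82.4% with 41 subjects and 86.8% with 46, and this point does not depend on it.

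**Step 1: the rule.** Let M be the number of major criteria met and m the number of minor ones. Progression holds if M ≥ 2, or M ≥ 1 and m ≥ 2, or m ≥ 3. With growing EMD as the only major criterion (M = 1):

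| Minor criteria met (m) | Result |
|---|---|
| 0 | not progression |
| 1 | not progression |
| 2 or more | progression |

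Of the 2^4 = 16 patterns of the four minor criteria, 1 + 4 = 5 are not progression. A second major criterion always gives progression. So 5 of all 2^6 = 64 patterns that include EMD growth are non-events. These are counts of patterns, not probabilities. EMD growth with few or no blood or marrow changes, the course at issue in EMD-only disease, falls among the 5.

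**Step 2: direction.** Compare the current rule with one that also counts PMD/PD.
- If the subject stays on study, the recorded event comes at the same time, later or never.
- If the subject changes therapy after the scan, a time that would have been an event becomes a censored time. Recoding an event as censored at the same time leaves the Kaplan-Meier curve equal or higher everywhere.

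Both routes point the same way.

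**Step 3: illustrative size.** The assumptions are mine, because the documents give neither the number of EMD-only subjects nor a PFS median: N = 46, exponential times with the same hazard in all subjects, and k EMD-only subjects.

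*Route A, censored when the event would have occurred.* If a share c of the k subjects' events still counts (deaths always do, as does EMD growth with enough other criteria), the hazard that Kaplan-Meier estimates falls by the factor 1 − k(1 − c)/46. So estimated median = true median × 46 / (46 − k(1 − c)).

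| True median | k | No events count (c = 0) | Half count (c = 0.5) |
|---|---|---|---|
| 12 months | 2 | 12 × 46/44 = 12.5 | 12 × 46/45 = 12.3 |
| 12 months | 5 | 12 × 46/41 = 13.5 | 12 × 46/43.5 = 12.7 |
| 12 months | 9 | 12 × 46/37 = 14.9 | 12 × 46/41.5 = 13.3 |
| 6 months | 9 | 6 × 46/37 = 7.5 | 6 × 46/41.5 = 6.7 |

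The c = 0 column is the ceiling for this route, since it removes deaths too.

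*Route B, kept at risk as event-free.* With EMD-only share q and counted hazard equal to a fraction f of the true hazard λ, the median t solves (1 − q)·exp(−λt) + q·exp(−fλt) = 0.5. For a true median of 12 months:
- q = 5%, f = 0.5: 12.4 months
- q = 10%, f = 0.5: 12.8 months
- q = 10%, f = 0: 14.0 months
- q = 20%, f = 0.5: 13.6 months

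If no EMD-only subject has isolated EMD growth, the effect is zero by either route.

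**The case against.** **Central review may already cover this.** Under Protocol 7.6 the committee judges response by criteria specific to the baseline category, and SAP 7.4 analyses centrally assessed PFS and durations. That may close the gap for central assessment. Whether it does depends on a charter that is not among the documents, and those analyses do not govern the investigator-assessed secondary endpoints.

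**The affected group may be small.** Inclusion criterion 3 requires relapsed or refractory subjects to have cytogenetic or hematological disease, which narrows the EMD-only group. It does not empty it: the category is listed, and disease evidence at entry does not make later EMD growth alone count.

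**The rule is deliberate and the endpoints are descriptive.** Protocol 1.1.2 says the criteria were adapted from published MDS/MPN criteria. SAP 7.1 states no hypothesis, and Protocol 4.2 rules out comparison with historical controls. This limits the consequence. It does not explain why Table E2 defines a progression category that the overall definition never uses.

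**A stronger reading to avoid.** A reader might infer that EMD-only subjects can never be recorded as progressing on growing EMD, and that PFS is therefore overstated. The documents do not support this. EMD growth with a second major criterion or two minor criteria is progression, death always counts, and the number of subjects concerned is not given.

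**Conclusion.** The gap is real for the investigator-assessed endpoints. Followed exactly, the plan does not count isolated extramedullary growth as progression, and it does not say how PMD/PD relates to overall progression. PFS and duration of response in EMD-only subjects, and hence the pooled estimates, target the same or longer times than if PMD/PD counted. Duration of CR ends on the same progression definition, so the same direction applies to it.

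Only the direction rests on the text. The size does not: under the assumptions shown, a 12-month median would read about 12.3 to 14.9 months by the censoring route with 2 to 9 subjects affected, and the effect could be nil. The CR-rate primary endpoint does not use the progression definition in this way and is unaffected. If some investigators record overall progression from PMD/PD alone, the event definition varies between sites, which also needs settling.

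**What to change.** **Analysis.** Add to SAP 7.3 a supportive investigator-assessed analysis of PFS and duration of response. In EMD-only subjects it would count the first Table A2 PMD/PD as an event, in addition to progression by Table A1 and death. State how EMD-only status is assigned (for example, the baseline category adjudicated under Protocol 7.6) and report the number of such subjects. The main analysis stays as it is.

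**Cost.** One extra run and table. Protocol 7.6.3 already schedules the imaging, and SAP Appendix C already lists target, non-target and new lesions and the investigator's EMD response (Listings 2.6.5 to 2.6.8). The downside is that the supportive estimates may be slightly less favourable.

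**Reconciliation.** The sponsor should reconcile Table E1/A1 with Table E2/A2 on how PMD/PD relates to overall progression. This review does not propose the rule: under Protocol 5.5.1 reported progression requires withdrawal from study treatment, so changing the definition would change clinical management.
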